8.1.1. Populations to be analysed

The statistical analysis will follow an intention-to-treat approach (i.e., will include data from all participants randomised into the study, regardless of whether they received the study intervention). This approach preserves the prognostic balance in the study arms achieved by randomisation.

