10.4. Visits and associated procedures

Clinical evaluations are intended to be performed by the same clinician throughout the study, whenever possible. If it is not possible to use the same evaluator to follow the patient, then evaluations should ideally overlap (i.e., examine the patient together and discuss findings) for at least one visit.

Visit 1 (including Screening), The University of Melbourne, 2 hours

The following procedures will be performed at Visit 1

- Written informed consent
- Demographic information
- Medical and ophthalmic histories
- Inclusion/exclusion criteria assessment
- Pre-treatment adverse event assessment
- Diet questioning
- Urine pregnancy test (for females of childbearing potential only)
- Habitual/ best corrected visual acuity
- MNSI questionnaire
- OSDI questionnaire
- EQ-5D-5L questionnaire
- iMTA questionnaire
- Tear osmolarity
- Basal (non-stimulated) tear collection
- Non-contact aesthesiometry

nPROOFS1-v1.2 [01-July-2018] Page 30 of 53

- Slit lamp assessment
- Anterior chamber angle assessment
- TRUT
- Ocular surface staining (Oxford scale)
- IOP (with anaesthesia and fluorescein using a Goldmann tonometer)
- Corneal confocal microscopy (with anaesthesia)
- Dilated fundus examination (with mydriatic eye drops) and non-invasive retinal imaging
- Pin-prick blood sample for omega-3 fatty acid analysis
- Re-check all eligibility requirements
- Dispense masked study products (if the participant meets the required qualifications)

Randomised participants will be provided with a supplement intake log (to mark off when they consume their supplements each day), given instructions with regard to how to take their supplements and be advised about the dose regimen to be followed. The supplement label (which specifies details with regard to: optimal storage conditions, clinical trial use only, keep out of reach of children, etc.) should also be read through and explained with the participant.

Participants will be asked to commence taking oral supplements (Day 1) on the day that their baseline nerve functions tests are conducted at Visit 2.

Visit 2 (Day 1; St Vincent's Hospital, 2 hours)

This visit will assess peripheral nerve fibre function, as per routine nerve conduction examinations, for diabetic neuropathy. The following procedures will be performed at this visit:

- Brief medical history (including related neuropathy symptoms)
- Michigan Diabetic Neuropathy Score
- Cutaneous silent period testing

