10.5. Instructions to eligible participants

Eligible participants will be asked to attend a total of 6 study visits; four visits will be at the University of Melbourne, and two will be performed at St Vincent's Hospital (at the start and end of the supplementation period), within four weeks of the initial and final visits.

At Visit 1, eligible participants will be dispensed study products consisting of their randomised treatment allocation. Study investigators will counsel the participant to consume 2 capsules each day, with or without food, at least two hours before or after medications. Participants will be provided with a supplement log to document their consumption of capsules each day. Participants will be advised not to 'make up' for missed doses with additional capsules on a given day; a reason for a 'missed dose' should be documented on the supplement log, which will be returned along with any remaining capsules at Visits 3, 4 and 6.

An appointment will be arranged for participants within four weeks of Visit 1, to attend Visit 2 at St Vincent's Hospital, Melbourne. Participants will be asked to start their first dose on the day of Visit 2 (Day 1), following their assessments at St Vincent's Hospital. Participants will be advised that they should maintain their regular dietary habits and medications (including ocular and systemic) and notify us of any change in medications of dosage throughout the study.

Appointments for Visits 2 and 5 at St Vincent's Hospital will be arranged for the participants by the study investigators, at Visits 1 and 4 respectively.

Participants will be encouraged to contact the Principal Investigator at any time should they have any questions about the study or the instructions they have been given.

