11.2.1. Michigan Neuropathy Screening Index

The Michigan Neuropathy Screening Index (MNSI) will be administered by the investigator (see below). Participants must score >3 in the two-part screening instrument, across both part A and part B, to be eligible for inclusion in the study. The physical assessment component (Part B) will be performed by a trained examiner.

Patient Version

MICHIGAN NEUROPATHY SCREENING INSTRUMENT

History (To be completed by the person with diabetes)		
Please take a few minutes to answer the following questions about the and feet. Check yes or no based on how you usually feel. Thank you.	feeling in y	our legs
1. Are you legs and/or feet numb?	□ Yes	□ No
2. Do you ever have any burning pain in your legs and/or feet?	□ Yes	□ No
3. Are your feet too sensitive to touch?	□ Yes	□ No
4. Do you get muscle cramps in your legs and/or feet?	□ Yes	□ No
5. Do you ever have any prickling feelings in your legs or feet?	□ Yes	□ No
6. Does it hurt when the bed covers touch your skin?	□ Yes	□ No
7. When you get into the tub or shower, are you able to tell the		
hot water from the cold water?	☐ Yes	□ No
8. Have you ever had an open sore on your foot?	□ Yes	□ No
9. Has your doctor ever told you that you have diabetic neuropathy?	□ Yes	□ No
10. Do you feel weak all over most of the time?	□ Yes	□ No
11. Are your symptoms worse at night?	□ Yes	□ No
12. Do your legs hurt when you walk?	□ Yes	□ No
13. Are you able to sense your feet when you walk?	□ Yes	□ No
14. Is the skin on your feet so dry that it cracks open?	□ Yes	□ No
15. Have you ever had an amputation?	□ Yes	□ No
Tota	al:	

nPROOFS1-v1.2 [01-July-2018] Page 45 of 53

A.

MICHIGAN NEUROPATHY SCREENING INSTRUMENT

B.	Physical Assess	ment (To b	be completed by h	ealth professio	onal)			
	1. Appearance	of Feet						
		Right				Left		
	a. Normal	□ 0 Ye	es 🗆 1 No		Normal	□ o Yes □	No	
	b. If no, ch	neck all tha	t apply:		If no, check	all that apply:		
	Deformities	3			Deformities			
	Dry skin, ca	allus			Dry skin, cal	lus		
	Infection				Infection			
	Fissure				Fissure			
	Other				Other			
	specify:				specify:			
			Right			Left		
2	TT1	Abs					esent	
2.	Ulceration] o		L] ₀ [1	
			Present/			Present/		
3.	Ankle Reflexes	Present	Reinforcement	Absent	Present	Reinforcement	Absent	
3.	Alikie Reliexes		□ 0.5		□0	□ 0.5	П 1	
		Present	Decreased	Absent	Present	Decreased	Absent	
4.	Vibration perception at great toe	□ o	□ 0.5	□ 1	□ 0	□ 0.5	□1	
5.	Monofilament	Normal	Reduced	Absent	Normal	Reduced	Absen	

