11.3 Basic blood samples

Blood tests to assess diabetes control will be performed, including fasting blood sugar level and HbA1c. Patients that have any disorder other than diabetes that could cause symptoms or signs of peripheral neuropathy will be excluded from participating. Thus, participants will be tested for B12 levels, folate levels, lipid profile, inflammatory markers (CRP, ESR), liver function and electrolytes.

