The statistical analysis aims to include all available data for all participants fulfilling all of the eligibility criteria. For the analyses of efficacy variables, participants will be included in the group to which they were randomised (i.e., as-randomised), referred to as the Intention-To-Treat sample. For the analyses of safety variables, participants will be included in the group they were treated (as-treated, if different from the randomised group assignment), referred to as the Safety sample.

Inclusion criteria

The following are the inclusion criteria for participant eligibility at Visit 1 (Baseline):

- 1. Male or female, \geq 18 years of age;
- 2. MNSI > 2;
- Written informed consent and documentation, in accordance with ethics requirements and ICH Good Clinical Practice (GCP), obtained prior to performing any study procedures;
- 4. Distance best corrected visual acuity of at least 6/12 Snellen equivalent in each eye using a standard logMAR visual acuity chart, measured at 3 metres;
- Intraocular pressure (IOP) ≤ 21 mmHg in both eyes, measured using applanation tonometry;
- 6. Ability to understand and follow study instructions, with the intention of completing all required study visits.

Exclusion criteria

The following are the exclusion criteria for participant eligibility at Visit 1 (Baseline):

Systemic

 Any uncontrolled systemic disease, other than sub-optimally controlled type-1 diabetes mellitus;

- Confirmed neuropathy secondary to causes other than diabetes (e.g., alcohol polyneuropathy, Vitamin B-12 deficiency, folate deficiency, chronic renal failure, hypothyroidism, neurotoxic drug use including chemotherapy);
- Any of the following general medical conditions: bipolar disorder, atrial fibrillation, implanted defibrillator, familial adenomatous polyposis, systemic immunocompromise;
- 4. A scheduled or planned systemic surgery over the course of the study;
- 5. Any known bleeding disorders;
- 6. Current consumption of a systemic anti-coagulant medication other than aspirin;
- 7. Females who are currently pregnant or breastfeeding;
- 8. Females of childbearing potential who are planning a pregnancy over the course of the study;
- Inability to sit/lie supine comfortably during the examination procedures for any reason.

Ophthalmic

- 10. Known allergy to, or previous reaction to, any ocular agents used in the study (i.e., ocular anaesthetics, sodium fluorescein, lissamine green, ocular mydriatics);

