0.5 - <1.0	3 [14%]	4 [21%]		5 [24%]		3 [14%]	4 [22%]		2 [11%]			0.057		0.16	
$1 \cdot 0 - < 1 \cdot 5$	1 [5%]	0 [0%]	••	3 [14%]	••	1 [5%]	3 [17%]	••	0 [0%]						
$ \begin{array}{l} 1 \cdot 5 - < 2 \cdot 0 \\ 2 \cdot 0 - 2 \cdot 5 \end{array} $	1 [5%] 1 [5%]	1 [5%] 0 [0%]		1 [5%] 0 [0%]	••	1 [5%] 1 [5%]	0 [0%] 0 [0%]		1 [5%] 0 [0%]						

Supplementary Tables and Figures

Page 14 of 16

2.5-<3.0	1 [5%]	0 [0%]	• •	0 [0%]	••	0 [0%]	0 [0%]	••	0 [0%]	• •
>3.0	0 [0%]	0 [0%]	• •	0 [0%]		0 [0%]	0 [0%]	• •	0 [0%]	••

Mean and standard deviation, unless stated otherwise. All values are derived from the average value of two eyes, unless otherwise indicated. IQR=interquartile range. PUFAs=polyunsaturated fatty acids.

^a p-values are not adjusted for multiple testing.

^b Estimates are presented as geometric mean ratio of the change from baseline in Omega-3 PUFAs vs Placebo at day 180

^c p-value for treatment comparison in change from baseline values was derived using the Wilcoxon rank sum test. Estimates and 95% confidence intervals at days 90 and 180 were derived using Hodges-Lehman non-parametric estimator.

^d Number of participants analysed for phenol red thread test in the treatment group was n=21 at baseline, n=19 at day 90 and n=19 at day 180; number analysed in the placebo group was n=22 at baseline, n=18 at day 90 and n=17 at day 180. Estimates for between-group change derived from n=43

^e Using the Efron grading scale

Estimate and 95% CI are presented as geometric mean ratio of the change from baseline in Omega-3 PUFAs vs Placebo at day 180, after accounting for imbalance at baseline in the statistical analysis model.

Table S10. Safety outcome: blood pathology parameters at baseline and day 180 (Safety sample)

		Omega-3 PUF	As		Placebo	Omega-3 PUFAs vs Placebo		
	Baseline $(n=21)$ Day 180 $(n=20)$ Change from baseline at day 180 $(n=20)$		Baseline (n=19)	Day 180 (n=16)	Change from baseline at day 180 (n=16)	Estimate (95% CI) Day 180 (n=40)	p- value ^a	
Haemoglobin (HB) (g/L)	140.5 (9.3)	139.8 (11.4)	-0.7 (5.9)	141.7 (10.8)	139.7 (15.3)	-1·3 (7·9)	1.0 (-3.5,5.4)	0.67
Platelets (x10 ⁹ /L)	259.2 (40.3)	257.0 (47.8)	-2.3 (20.1)	244.5 (57.3)	251.6 (64.5)	9.6 (30.5)	-10-2 (-26-6,6-3)	0.23
HbA1c (%)	7.34 (0.81)	7.44 (0.79)	0.10 (0.51)	7.82 (1.11)	7.81 (0.94)	0.13 (0.54)	-0.11 (-0.42,0.21)	0.50
Alkaline phosphatase (ALP) (U/L)	75.3 (18.0)	76.6 (19.6)	1.2 (7.4)	79.1 (26.0)	83.4 (33.3)	6.5 (11.3)	-4.9 (-10.9,1.1)	0.11

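### SAP section 3 limits its Intention-To-Treat data to participants who meet every eligibility criterion, contradicting the protocol's all-randomised definition and allowing removal on information obtained after allocation

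*Combined protocol and SAP*

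**What the plan says.** Protocol 8.1.1 states that the intention-to-treat analysis "will include data from all participants randomised into the study, regardless of whether they received the study intervention". It sets no eligibility condition.

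SAP section 3 (Analysis sets/Populations) begins: "The statistical analysis aims to include all available data for all participants fulfilling all of the eligibility criteria". For efficacy it then says that "participants will be included in the group to which they were randomised (i.e., as-randomised), referred to as the Intention-To-Treat sample". The inclusion and exclusion lists follow.

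On timing:
- **Allocation.** Protocol 10.5 says "At Visit 1, eligible participants will be dispensed study products consisting of their randomised treatment allocation". Protocol 10.4 places an eligibility re-check and dispensing at the end of the Visit 1 list.
- **Bloods.** Protocol 7.1 places the blood tests at Visits 2 and 5. Protocol 11.3 ties them to eligibility: "Patients that have any disorder other than diabetes that could cause symptoms or signs of peripheral neuropathy will be excluded from participating". This corresponds to exclusion criterion 2.
- **MNSI.** Protocol 11.2.1, within the hospital tests of Visits 2 and 5, says: "Participants must score >3 in the two-part screening instrument, across both part A and part B". The inclusion lists in protocol 2.4.3 and SAP section 3 give a cut-off of >2.

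**The concern.** Analysing people in the arm to which they were randomised settles which arm each person counts in. It does not bring back someone whom the preceding sentence has left out. The SAP defines no all-randomised set anywhere else, so its efficacy set is narrower than the protocol's although it carries the same name.

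This would do little harm if every criterion were settled before allocation, because nobody randomised could then fail one except through error. Here at least one criterion, and apparently two, rest on tests scheduled after allocation. At stake is whether the primary CNFL comparison is made on everyone randomised or on a subset chosen afterwards. The SAP gives no rule on who judges eligibility, from which records, or by what date.

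**Working it through.** **1. Order of events, from the protocol**

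| Step | When | Where stated |
|---|---|---|
| Eligibility re-check, allocated product dispensed | Visit 1 | 10.4, 10.5 |
| Bloods serving exclusion 2 | Visit 2 (Day 1) | 7.1, 10.4, 11.3 |
| Two-part MNSI serving inclusion 2 | Described under the Visit 2 and 5 tests | 11.2, 11.2.1 |
| First dose | Day of Visit 2, after the assessments | 10.5 |

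The marks in the visit-schedule table did not survive text extraction, so allocation at Visit 1 is read from 10.4 and 10.5.

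**2. Which criteria are affected**

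Two numbered criteria. Exclusion 2 covers several causes that a laboratory can test. For inclusion 2 the timing is inconsistent: 10.4 lists the MNSI questionnaire at Visit 1 and omits the MNSI from Visit 2, while 6.2, 11.2.1 and SAP section 1 place the instrument at the hospital.

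**3. MNSI cut-off**

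Part B is scored in half points. Totals of 2.5 and 3 therefore satisfy >2 and fail >3, so those participants are eligible under one passage and ineligible under another.

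**4. Sample size and power**

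Inputs from protocol 2.4.1: difference 2.9 mm/mm², SD 3.2, two-sided alpha 0.05, power 80%.
- Normal approximation: n = 2 × (1.96 + 0.84)² × (3.2/2.9)² ≈ 19.1, rounded up to 20 per group.
- Two-sample t-test: n = 20.12, rounded up to 21. This matches the plan.
- Attrition: 21/0.85 = 24.7, rounded up to 25. This also matches.

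Power of the same t-test after removals (the number removed is an assumption):

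| Analysed | Removed from 43 | Power |
|---|---|---|
| 21 v 22 | 0 | 82.7% |
| 20 v 19 | 4 | 78.7% |
| 18 v 19 | 6 | 76.4% |

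These figures ignore baseline adjustment and dropout, so they show only the order of the loss.

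**5. Do the results show removal?**

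The efficacy tables (for example Table S4) have baseline n = 21 and n = 22, with estimates on 43. That equals the reduced target in SAP section 1. One omega-3 participant without limb nerve tests is still among the 21. The appended list of changes from the planned analysis mentions no eligibility exclusion. The number randomised would appear in the CONSORT figure, which is not shown.

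**The case against.** The strongest reply is that the opening SAP sentence only describes who was enrolled. Its verb is one of aim, the lists are headed as applying at Visit 1, the protocol randomises only people judged eligible, and the only data set the SAP plans with exclusions is the one for non-compliance. That is a fair reading of intent. It does not cure the text: the sentence heads the section that defines the analysis sets, and a participant allocated at Visit 1 and found ineligible from Visit 2 bloods falls outside it.

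The reply is right to limit the harm. Both sets of tests precede the first dose, so treatment cannot influence them. Protocol 3.7.1 masks investigators, assessors and analysts. No route by which exclusions would differ systematically between arms is evident.

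Three stronger inferences are tempting and are not supported.
- **Table S10 shows 3 of 43 unverified, all on placebo.** The table heads its baseline columns 21 omega-3 and 19 placebo, against 22 in the placebo arm. It reports no B12 or folate, and its counts vary: placebo eGFR sums to 11 + 4 = 15. It does carry TSH and eGFR, but exclusion 2 requires confirmed neuropathy from another cause, and a missing result is not that. Out-of-window results are also set to missing under SAP section 5. These counts do not measure ineligibility.
- **Protocol 10.6 permits deletion of data.** It lets the principal investigator discontinue a wrongly enrolled participant. It says nothing about removing data from analysis.
- **Participants were in fact removed.** Nothing reported shows this. It can be neither asserted nor fully excluded without the number randomised.

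**Conclusion.** The conflict between SAP section 3 and protocol 8.1.1 is real, and the SAP text is wrong as written. It allows post-allocation removal of randomised participants under two numbered criteria, with no rule on who decides or on what data. The principal harm is loss of the all-randomised comparison, followed by some precision: about 4 points of power for four assumed removals and about 6 for six (82.7 − 78.7 = 4.0; 82.7 − 76.4 = 6.3). Bias between arms is not demonstrated, and the reported 43 are consistent with nobody having been removed.

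Confidence is high on the wording conflict and on the timing of the bloods. It is lower on the timing of MNSI Part B, where the protocol disagrees with itself.

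**What to change.** 1. In SAP section 3, define the Intention-To-Treat set as all randomised participants, analysed as randomised, in line with protocol 8.1.1.
2. List eligibility deviations found after allocation, without excluding anyone for them.
3. Confine any eligibility-based exclusion to a sensitivity analysis. State who decides, from which records, and that the decision is made under masking.
4. Report the number randomised against the number analysed in each arm, and account for any difference.
5. Reconcile the MNSI entry cut-off between protocol 2.4.3 and SAP section 3 (>2) and protocol 11.2.1 (>3), together with the visit at which the two-part score is obtained.

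The cost is a few sentences in a dated clarification and one line in the participant flow. If the 43 are everyone randomised, no result changes; if not, the efficacy models need rerunning with the missing participants' available data. The last visit was on 10 March 2020 and the SAP is dated 30 June 2020, so moving randomisation to after Visit 2 is no longer possible.

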7.1.1 Multiple testing

The primary outcome at day 180 will be evaluated using the two-sided 5% level of significance.

Multiple testing for the key secondary outcomes related to corneal nerve parameters at day 180 will be assessed using the Benjamini-Hochberg stepwise method with a false discovery rate of 5% for: corneal nerve fibre density (CNFD), corneal nerve branch density (CNBD), central corneal sensitivity thresholds to room temperature, and central corneal sensitivity thresholds to cooled temperature. For these key secondary outcomes at day 180, we will report the multiplicity adjusted p-values.

For all other post-baseline time points and outcomes, we will report multiplicity unadjusted p-values. Given the large number of statistical tests, the probability of finding at least one false positive finding will be close to 100%. For this reason, we will exercise caution and in addition to p-values, associations will be interpreted based on the magnitude and direction of the association and width of the 95% confidence intervals.

All tests will be performed two-sided, and we will report two-sided 95% confidence intervals.

8. Sensitivity Analyses

Additional sensitivity analyses will be performed for the outcomes linked to the primary and key secondary aims for the following dataset:

- Dataset excluding participants deemed non-compliant (see definition in Section 6.3).

9. QC Plans

Source data verification of the data entered on REDCap was performed by the Principal Investigator (PI). Data was manually checked for accuracy from the source worksheets/original digital data record, for all participants, for the primary outcome (CNFL) and key secondary outcomes (CNFD, CNBD, central corneal sensitivity thresholds to room temperature, and central corneal sensitivity thresholds to cooled temperature). In addition, a subset of data comprising at least 20% of the full dataset,

was randomly selected by the PI for verification, to ensure that the observations and findings are recorded correctly and completely. Data found as incorrectly entered were verified against the original source documents, corrected on REDCap and recorded accordingly.

10. Programming Plans

A list of all planned tables and figures and their templates can be found in Appendix 4.

Tolerance windows will be used for converting visit dates into visit numbers according to the study visit schedule before summarising or analysing the data. The relative day of testing will be derived as the visit date minus the supplementation start date. The visit windows in Table 1 will be applied to the testing dates.

Table 1. Visit windows

Visit	Target day	Lower limit (incl.)	Upper limit (incl.)
Day 1	Supplement start date (Day 0)	Day -35	1
Day 30	Day 30	Day 14	Day 44
Day 90	Day 90	Day 76	Day 104
Day 180	Day 180	Day 156	Day 204

Assessments performed outside of these visit windows will not be included in the analyses. If a participant has more than one assessment performed within the same visit window, then the assessment closest to the target date will be used. The visit windows will be applied to the study variables described in Appendix 1.

